**Figure 4-1 Study Design Schematic: Part 1**

Screening	Check-in	Dosing a	LOXO-292 and Total Radioactivity Concentrations, and MetID Sampling	Clinic Discharge b	Safety Follow-up Call c
Days -29 to -2	Day -1	Day 1	Day 1 to Clinic Discharge	Days 8 to 22	Approximately 7 days after Clinic Discharge
Clinic Confinement					

MetID = metabolite profiling and identification

a Single oral dose of 160 mg of [C]-LOXO-292 (~40 µCi) administered as an oral solution following an overnight fast.

b Subjects will be discharged from the Clinical Research Unit (CRU) starting on Day 8 if ≥ 90% of the radioactive dose is recovered and ≤ 1% of the radioactive dose per day is recovered in excreta (urine and feces) for 3 consecutive days on which a fecal sample is collected. If these criteria are not satisfied by the morning of Day 8, subjects will continue to be confined in the CRU until these criteria are met, up to a maximum of Day 22.

c Subjects will receive a Safety Follow-up Call approximately 7 days after Clinic Discharge.

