**Part 1:**

After a Screening period of up to 28 days, subjects will check in to the Clinical Research Unit (CRU) on Day -1 to confirm eligibility and to become familiar with study procedures. On the morning of Day 1, following an overnight fast of at least 8 hours, subjects will receive a single oral dose of 160 mg of [C]-LOXO-292 (containing ~40 µCi) administered as an oral solution. Subjects will be confined at the CRU from the time of Check-in until Clinic Discharge (between Days 8 and 22). After completing discharge procedures, subjects will be discharged from the CRU as early as Day 8 and up to Day 22, provided recovery of radioactivity has reached the following threshold values:

- $\geq 90\%$  of the radioactive dose is recovered, and
- $\leq 1\%$  of the radioactive dose per day is recovered in excreta (urine and feces) for 3 consecutive days on which a fecal sample is collected.

Sample collection and confinement will continue until discharge criteria are met or the maximum stay is reached, unless otherwise agreed upon by the Sponsor and Investigator (or designee). Subjects will receive a Safety Follow-up Call approximately 7 days after Clinic Discharge.

Safety will be monitored with AE inquiries, clinical laboratory evaluations (Appendix A), vital signs measurements, 12-lead ECGs, and physical examinations during the study.

Samples for determination of LOXO-292 concentrations in plasma, total radioactivity concentrations in plasma, whole blood, urine, and feces, and for metabolite profiling/characterization will be obtained through at least 168 hours postdose (Day 8), and possibly up to 504 hours postdose (Day 22). A Schedule of Assessments for Part 1 is presented in Table 6-1.

In Part 1, for subjects experiencing emesis within 2 hours following dosing, vomitus will be collected. That subject may be considered not evaluable and the Medical Monitor (or designee) should be contacted immediately for further instructions and to determine if the subject should continue the study. All vomitus collected will be stored for possible analysis.

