- b Subjects who withdraw from the study prior to meeting discharge criteria should undergo all discharge tests and assessments at ET, and will receive a Safety Follow-up Call approximately 7 days after ET.
- c A full medical history will be recorded at Screening. An interim medical history update will be recorded on Day -1.
- d Height and BMI will be measured at Screening only.
- e Drug urine screen (which includes cotinine) will be conducted at Screening and at Check-in (Day -1). An alcohol breath test will be conducted at Check-in only.
- f A complete physical examination will be conducted at Screening and at Clinic Discharge/ET. An abbreviated physical examination (general, heart, lungs, abdomen, and skin) will be conducted at Check-in.
- g Every attempt will be made to ensure blood samples for the clinical chemistry panel are collected following a fast from food for at least 8 hours. Test for TSH will be performed at Screening only. Other clinical laboratory evaluations will be conducted at Screening, Check-in, on Day 4, and at Clinic Discharge/ET.
- h Subjects are to remain supine for at least 5 minutes prior to vital signs measurements. Vital signs will be obtained at Screening; Check-in; on Day 1 predose and 2 hours postdose; and daily (24-hour intervals) up to and including day of Clinic Discharge/ET. When scheduled at the same nominal times, postdose vital signs measurements are to be performed prior to postdose PK blood draws (see [Section 6.5](#)), with blood draws occurring as close to the nominal times as possible.
- i Subjects are to remain supine for at least 5 minutes prior to ECG assessments. The ECGs will be obtained at Screening and Check-in, on Day 1 predose, 2 hours postdose, and at Clinic Discharge/ET. When scheduled at the same nominal times, postdose ECGs are to be performed prior to postdose vital signs measurements and PK blood draws (see [Section 6.5](#)), with blood draws occurring as close as possible to the nominal times.

j CCI

- a AEs, SAEs, and concomitant medications and procedures will be monitored and recorded throughout the study from the time of signing the informed consent, as described in [Section 6.5.1](#), [Appendix C](#), and [Section 6.3.2](#). A "How Do You Feel?" AE inquiry will be performed at Screening, Check-in, each vital signs measurement, and during the Safety Follow-up Call.

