9 DEFINITION OF ANALYSIS POPULATIONS

The **Safety Populations** for Parts 1 and 2 will consist of all subjects who received at least 1 dose of study treatment and have at least 1 post-dose safety assessment.

The **PK Populations** for Parts 1 and 2 will consist of all subjects who received at least 1 dose of study treatment and have evaluable PK data.

Data for each subject will be included in the summary statistics and statistical comparisons of PK parameters with the exceptions described as follows:

- Data from subjects who experience emesis at or before 2 times median T_{max} for the given treatment may be excluded from the summary statistics and data presentation of PK parameters for the given treatment.
- Data from subjects who significantly violate protocol inclusion or exclusion criteria, deviate significantly from the protocol, or have unavailable or incomplete data which may influence the PK analysis will be excluded from the PK Population.

Any subject or data excluded from the analysis will be identified, along with their reason for exclusion, in the CSR.

The **All Subjects Populations** for Parts 1 and 2 will consist of any subjects who enrolled on to the study (signed informed consent, met all inclusion and exclusion criteria, and had study assessments recorded on the database as per the protocol).

All protocol deviations that occur during the study will be considered prior to database lock for their severity/impact and will be taken into consideration when subjects are assigned to analysis populations. Details of subject assignment to the analysis populations will be listed.

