10 STATISTICAL METHODOLOGY

10.1 General

Data listings will be provided for the All Subjects Populations for Parts 1 and 2. Summary statistics will be performed for subjects included in the relevant analysis populations (Safety/PK).

For continuous data, summary statistics will include the arithmetic mean, arithmetic standard deviation (SD), median, minimum (Min), maximum (Max), number of subjects (N), and number of observations (n). For log-normal data (e.g., the PK parameters: areas under the concentration-time curve [AUCs] and maximum observed concentration [C_{max}]), the geometric mean and geometric coefficient of variation (CV%) will also be presented. For categorical data, frequency counts and percentages will be presented. Data listings will be provided for all subjects up to the point of withdrawal, with any subjects excluded from the relevant population highlighted. For the calculation of summary statistics and data presentation, unrounded data will be used.

Missing values will not be imputed, with the exception of missing PK predose concentrations, which may be set to zero for PK analysis, with Sponsor approval (see Section 0).

Data analysis will be performed using SAS® Version 9.4 or higher.

Analysis Data Model (ADaM) datasets will be prepared using Clinical Data Interchange Standards Consortium (CDISC) ADaM Version 2.1, and CDISC ADaM Implementation Guide Version 1.1. Pinnacle 21 Community Validator Version 2.2.0 will be utilized to ensure compliance with CDISC standards.

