Blood/Plasma AUC Ratio	AUC _{0-∞} of total radioactivity in whole blood / AUC _{0-∞} of total radioactivity in plasma
Plasma LOXO-292 / Total Radioactivity AUC Ratio	AUC _{0-∞} of LOXO-292 in plasma / AUC _{0-∞} of total radioactivity in plasma.

The AUC ratios (AUC total radioactivity in whole blood to AUC total radioactivity in plasma, and AUC of Plasma LOXO-292 to AUC of plasma total radioactivity) will be based on AUC_{0-∞}. Where AUC_{0-∞} cannot be reliably calculated, an alternative AUC measure, such as AUC_{last} or AUC to a common timepoint, may be used.

Additionally, blood-to-plasma concentration ratios at each sampling timepoint will be calculated (by the Covance Radioanalysis Department) and reported in the radioanalysis report to determine partitioning of total radioactivity into red blood cells.

In addition, for each subject, the following PK parameters will be calculated whenever possible, based on the urine concentrations of total radioactivity:

Parameter	Definition
A _{eu}	amount excreted in urine per sampling interval
Cum A _{eu}	cumulative amount excreted in urine
%f _{eu}	percentage of dose excreted in urine per sampling interval, where %f _{eu} = 100 (A _{eu} /dose)
Cum %f _{eu}	cumulative percentage of dose excreted in urine.

For each subject, the following PK parameters will be calculated whenever possible, based on the fecal concentrations of total radioactivity:

Parameter	Definition
A _{ef}	amount excreted in feces per sampling interval
Cum A _{ef}	cumulative amount excreted in feces
%f _{ef}	percentage of dose excreted in feces per sampling interval, where %f _{ef} = 100 (A _{ef} /dose)
Cum %f _{ef}	cumulative percentage of dose excreted in feces

All PK parameters for total radioactivity in urine and feces will be calculated by the Covance Radioanalysis Department and will be reported in the radioanalysis report. The Covance Radioanalysis Department will also calculate and report the amount of total radioactivity in total excreta (feces + urine).

The amount excreted in urine or feces (A_{eu} or A_{ef}) for each collection interval will be calculated as the product of concentration and sample weight; Cum A_{eu} and Cum A_{ef} will be calculated by summing the A_{eu} or A_{ef} values for each collection interval.

The percentage of the dose excreted in urine or feces (% f_{eu} or % f_{ef}) will be calculated for each collection interval (i) and cumulatively according to the following formula:

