Cum $\%f_{eu}$	cumulative percentage of dose excreted in urine

For each subject, the following PK parameters will be calculated, whenever possible, based on the fecal concentrations of total radioactivity:

Parameter	Definition
A_{ef}	amount excreted in feces per sampling interval
Cum A_{ef}	cumulative amount excreted in feces
$\%f_{ef}$	percentage of dose excreted in feces per sampling interval, where $\%f_{ef} = 100 (A_{ef}/\text{dose})$
Cum $\%f_{ef}$	cumulative percentage of dose excreted in feces

The following excretion parameters will be calculated, whenever possible, based on total radioactivity in total (urine+feces) excreta:

Parameter	Definition
%f _e	percentage of dose excreted in urine and feces per sampling interval, where $\%f_e = \%f_{eu} + \%f_{ef}$
Cum %f _e	cumulative percentage of dose excreted in urine and feces, calculated as the sum of the percentage of dose excreted in urine and feces for each collection period

C_{max} and T_{max} will be obtained directly from the plasma and whole blood concentration-time profiles.

For multiple peaks, the highest postdose concentration will be reported as C_{max}. In the case that multiple peaks are of equal magnitude, the earliest T_{max} will be reported.

The amount excreted (A_e) in urine and feces for each collection interval will be calculated as the product of analyte concentration in urine or feces and sample weight. Cumulative A_e will be calculated by summing the A_e values for each collection interval over the sampling period.

10.3.2 Criteria for Handling Concentrations Below the Limit of Quantification in Pharmacokinetic Analysis

Concentration values that are below the limit of quantification (BLQ) will be set to zero, with defined exceptions as follows;

- Any embedded BLQ value (between 2 quantifiable concentrations) and BLQ values following the last quantifiable concentration in a profile will be set to missing for the purposes of PK analysis.
- If there are late positive concentration values following 2 BLQ concentration values in the apparent terminal phase, these values will be evaluated. If these values are considered to be anomalous, they will be set to missing.
- If an entire concentration-time profile is BLQ, the profile will be excluded from the PK analysis.
- If a predose concentration is missing, these values may be set to zero with Sponsor approval

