10.4.2 Presentation of Pharmacokinetic Parameters

For the calculation of summary statistics of PK parameters, all NR and NC values in a data series will be set to missing.

The AUC values will be set to NC if they have been calculated using fewer than three concentrations, and/or three concentrations if the last is C_{max} .

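### Does the SAP's no-imputation rule distort Part 1 mass balance when subjects leave on different days?

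*SAP*

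**What the plan says.** Part 1 plans six completers (SAP 6). From Day 8 a subject may leave once recovery has reached 90% of the radioactive dose and daily excretion is 1% or less on three consecutive days with a fecal sample. Otherwise "subjects will continue to be confined in the CRU until these criteria are met, up to a maximum of Day 22" (Protocol Figure 4-1, footnote b). Protocol 4.1 also lets the Sponsor and Investigator agree on a different stopping point. For early leavers, Table 6-1 footnote b says "Subjects who withdraw from the study prior to meeting discharge criteria should undergo all discharge tests and assessments at ET".

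On analysis, SAP 10.1 states "Missing values will not be imputed, with the exception of missing PK predose concentrations, which may be set to zero for PK analysis", and SAP 10.4.2 adds "For the calculation of summary statistics of PK parameters, all NR and NC values in a data series will be set to missing". SAP 10.3.1 lists the Part 1 excretion parameters for each subject: interval and cumulative amounts, and interval and cumulative percentages of dose, in urine and in feces. Cumulative amounts are sums over collection intervals. The radioanalysis group calculates and reports these, together with the amount in total excreta. After the Part 2 tables, the SAP defines the combined percentage as "cumulative percentage of dose excreted in urine and feces, calculated as the sum of the percentage of dose excreted" in the two matrices. SAP 10.4.3 plans descriptive statistics for PK parameters in both parts. SAP 9 removes from the PK Population subjects who "have unavailable or incomplete data which may influence the PK analysis will be excluded from the PK Population".

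**The concern.** The day on which a subject's collection stops depends on his recovery, which is the quantity being estimated. Intervals after discharge are therefore not missing at random. Neither document says how a discharged subject enters later intervals: carried forward, given a zero increment, or left out. A strict reader of SAP 10.1 would leave him out. The late means would then describe a subset selected by outcome, and the mean cumulative curve could fall, which no subject's own curve can do.

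Mass balance and routes of elimination are the first primary objective of Part 1. If recovery were read from the end of such a curve, both the total and the urine/feces split could rest on very few subjects. A second worry is that SAP 9 might be read to exclude a subject discharged under the rule, or that a total cut short by early exit might be averaged in without notice.

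**Working it through.** **Inputs from the documents.** Six subjects; the discharge thresholds above; a window of 168 to 504 h. The window agrees with the day numbering: 24 × (8 − 1) = 168 and 24 × (22 − 1) = 504. There is no power calculation to reproduce; Protocol 7.1 sets the sample size by precedent. SAP 6.1 omits the per-day qualifier on the 1% threshold that Protocol 4.1 and SAP Figure 6-1 carry. Those passages must be reconciled; the calculations here use the per-day form.

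**Step 1: the identity.** With *k* of six discharged, the late mean of those still confined minus the six-subject mean of final totals equals (*k*/6) × (mean of confined − mean of discharged). Take assumed final totals of 95, 94, 93 and 92 (discharged) and 82 and 80 (confined):
- six-subject mean: 536/6 = 89.3%
- mean of the two confined: 162/2 = 81.0%
- gap: (4/6) × (81.0 − 93.5) = −8.3 points.

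**Step 2: an example run through the discharge rule.** Assume cumulative recovery R × (1 − 2^(−(t−1)/h)), with t in days since dosing and (R, h) = (98, 0.9), (97, 1.0), (96, 1.1), (95, 1.5), (92, 2.2), (86, 2.5). Discharge falls on Days 11, 11, 12, 13, 16 and 22, with totals of 97.9, 96.8, 95.8, 94.4, 90.9 and 85.7.
- Mean of those still confined: 91.6% on Day 11 (n = 6), 89.6% on Day 12 (n = 4), 85.7% on Day 22 (n = 1).
- Mean of each subject's own total: 561.5/6 = 93.6%.
- Six-subject mean on Day 22 had all stayed: 93.9%.

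The late mean is 8.2 points low; the mean of own totals is 0.3 points low.

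**Step 3: the range.** Simulated six-subject trials with first-order excretion, median half-life 18 to 40 h and recovery SD 2 to 6 (all assumed). The gap is the mean at the last interval with any subject, minus the mean of own final totals.

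| Mean recovery | Average gap (points) | Trials in which the mean curve falls |
|---|---|---|
| 80-84% | −0.1 to −0.2 | 3-13% |
| 88-95% | −1.8 to −4.5 (−5.3 at mean 95, SD 6) | 86-99% |
| 97% | −0.4 to −1.7 | 80-93% |

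The gap is not always downward: it is upward in 0-23% of trials at 88-95% and in 22-42% at 97%. The −8.3 of Step 1 lies outside these averages because its totals are more spread out (SD about 6.6).

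**Step 4: which of these does the plan prescribe?**
- SAP 10.3.1 defines the Part 1 cumulative parameters subject by subject, as sums over collection intervals. A discharged subject's sum is complete on what was collected; no value has to be supplied.
- The closing text of SAP 10.3.1 takes that sum across the sampling period. The same block covers whole-blood profiles, and whole blood is assayed only in Part 1 (Protocol 6.4.5), so the text is not confined to Part 2.
- SAP Section 3 defines combined cumulative recovery without limiting it to Part 2. For Part 1 it also follows directly by adding the urine and feces percentages.
- No section promises a table or curve of Part 1 mean recovery by interval. SAP 10.3.1 and 10.4.1 place Part 1 excreta results in the radioanalysis report, whose summary rules are not among these documents.
- SAP 10.4.2 concerns values with no result or not calculated. It does not mention intervals never scheduled because the subject had been discharged. Protocol Appendix B, footnote a, treats fewer blood samples after early discharge as expected.

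**Step 5: the side issues.** SAP 6 counts a subject with sufficient sampling before discharge as a completer, so calling rule-based discharge incomplete data is strained. SAP 10.1 already requires the number of observations in continuous summaries. An early exit could matter: five subjects averaging 93.0% and one leaving at an assumed 70% give (5 × 93.0 + 70)/6 = 89.2% with him and 93.0% without. SAP 9 requires any exclusion and its reason to be stated in the study report, and SAP 10.2 lists disposition.

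**The case for a change.** The strongest case for a change is that the plan never names the Part 1 mass-balance figure, that SAP 10.1 and 10.4.3 are worded for both parts, and that a sentence in the SAP would remove the doubt before database lock at almost no cost. The silence is real, and so is the mechanism: at recoveries near or above 90%, where the discharge rule takes effect, a careless late mean would mislead.

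Two things limit this. The damage requires an analyst to choose a readout that the plan does not specify, and a falling mean cumulative curve with shrinking n in a six-subject study would be hard to miss. Carrying values forward is also not free of error, since it gives a lower bound. Under the Step 3 assumptions it misses 0.1 to 1.0 points per discharged subject on average. For a subject leaving on Day 8 while excreting 1% per day it misses about 1.0 to 5.8 points by Day 22, if that rate halves every 1 to 5 days. The miss cannot exceed 10 points, because 90% has already been recovered.

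**Conclusion.** No change is needed. Outcome-dependent stopping would bias late interval means, on average by 0.2 points or less at 80-84% recovery and by about 2 to 5 points at 88-95%, usually downward. All of these sizes rest on assumed excretion curves. The natural reading of SAP 10.3.1 with 10.4.3 instead gives each subject's recovery to his own last collection, averaged over the PK Population, and the selection does not touch that average. What remains unwritten is how a by-interval display, if one is made, treats discharged subjects. That is ordinary reporting detail for the radioanalysis group. The conclusion assumes that their report summarises subject totals, as the parameter definitions imply; it would change only if recovery were taken from a late-interval mean.

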10.1.1 Definition of Baseline and Change from Baseline

If changes from baselines are calculated, baseline for each parameter is defined as the last value measured prior to the first dose, including repeat (vital signs and electrocardiograms [ECGs]) and unscheduled (clinical laboratory parameters) readings (see Section 10.1.2 for definitions of repeat and unscheduled readings).

Mean change from baseline is the mean of all individual subjects' change from baseline values. Each individual change from baseline will be calculated by subtracting the individual subject's baseline value from the value at the timepoint.

10.1.2 Repeat and Unscheduled Readings

Repeat readings occur when the original vital signs or ECG result requires confirmation. Repeat readings are labelled as 'Repeat' in the listings and replace the original readings in all summaries and changes from baseline presentations and calculations. Prior to dosing, all readings taken in addition to the original reading are defined as predose repeats. Postdose repeat readings are defined as readings collected within 15 minutes of the actual time of the original reading.

With the exception of predose results described above, unscheduled readings for vital signs or ECGs are defined as readings collected >15 minutes from the actual time of the original reading. All results not taken at a scheduled timepoint for other data types (e.g., clinical laboratory parameters) are unscheduled. Unscheduled readings are labelled as 'Unscheduled' in the listings. Because unscheduled readings are not associated with any scheduled timepoint, they are excluded from all summaries with the exception that they may be used as baseline.

